## **h) Data Management and Confidentiality**

If a participant agrees to be in this study, we will collect health information that identifies them, “Protected Health Information” (PHI). We may collect the results of tests, questionnaires and interviews. We may collect information from a patient’s medical record. We will only collect information that is needed for the research. This information is described in the consent form. By signing the consent form a participant gives us permission (authorization) to collect, use and share their health information.

Data collected will include questionnaires and assessments as described above in section (5f). Labs and tests will be done at the ISMMS laboratory and information sent to the PI, data for these will be stored in a binder which will be secured in a double locked fashion. Blood samples will be labeled with de-identified codes, which cannot be associated with individual subjects. PHI, such as patient name and DOB, will only be included in a separate file including the consent documents. All other data collected for the study will be de-identified and stored apart from PHI, identified by study number linked to PHI in a secure file. This data will be stored indefinitely.

The PI will be responsible for receipt and transmission of study data and specimens. Quality control of the data collected will include double data entry and data quality check by investigators after each 5 subjects completed.

Study staff will have access to data and records may be reviewed by the Mount Sinai School of Medicine Institutional Review or government agencies (i.e. NIH) in order to meet federal or state research regulations. Please be aware that once private information is disclosed, it is subject to re-disclosure by the recipient and can no longer be considered protected. If research records are used for decisions related to clinical care, then a participant has the right to review this information and to request changes. This is limited to information about their treatment, and does not include information related to procedures or tests that are for research purposes only. Participants may access this information only after the study analysis is complete.

Data from this study may be used in medical publications or presentations. The information will be de-identified so that individual subjects cannot be recognized and the information will no longer be considered PHI. The information that is collected for research will be analyzed for many years and it is not possible to know how long this analysis and follow-up will take. Therefore, participants are allowing access to this information indefinitely.

Subjects will only be identified with a numerical code in compliance with HIPAA regulations. Raw subject data will be secured in double locked physical control. Digitized raw data will be similarly de-identified using coding and will be secured on an MS SQL server with Windows integrated security.

	Protocol Title:	A Molecular Approach to Treat Cognition in Schizophrenia: Ca 2+ Channel Blockade
	Principal Investigator Name/Contact Info:	[name] [contact]
	Primary Contact Name/Contact Info	[name] [REDACTED]
	Date Revised:	May 16, 2017
	Study Number:	HSM# 12-0031, GCO# 12-0679, GCO# 13-1987

Data analysis plan is included below. All analyses will be based on an intent-to-treat sample of subjects who received at least one dose of isradipine. Since the missing values may be dependent on the observed outcomes, we assume the missing data mechanism to be missing at random, and hence a mixed models analysis will be used to assess the treatment effect of isradipine with fixed effects for week and first order autoregressive covariance structure to evaluate change over time for all of the primary outcome measures. Cognitive measures will be handled differently, as these will only be collected at two time points – if missing data are substantial (or a complete visit is missing), subjects' data will not/cannot be meaningfully analyzed.

*Primary Analyses* will test the following hypotheses based on our specific aims:

To determine the feasibility of 4 weeks of isradipine on cognitive outcomes in SZ.  
Hypothesis: We will successfully recruit up to 80 stable schizophrenia and schizoaffective patients

To determine the safety of 4 weeks of isradipine on cognitive outcomes in SZ.  
Hypothesis: The frequency of new or worsened side effects (clinician-rated; self-reported; lab-based) will not be significantly different from baseline to end of study visit.

A Fisher exact test will compare time-points by frequencies of new or worsened (compared with baseline) side effect severity ratings – this will be done for all side effects assessed by the SEC.

Differences on laboratory measures (chemistry panel, etc.) will be tested using repeated measures ANCOVA (baseline and week 4) and changes in vital signs (specifically blood pressure) will be assessed using mixed model ANCOVA, to incorporate data at each weekly visit.

Differences on SAS and AIMS total scores will be examined by calculating the  $\tau$ -b rank correlation between score and week for each subject and comparing the distribution of these trend scores with the Conover-Salsburg rank test.

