### 1) Objectives:

In this project we propose to conduct a 4-week open label cognitive enhancement trial of isradipine in up to 80 stable outpatients with schizophrenia and schizoaffective disorder.

The primary aim of this study is to evaluate the effects of the calcium channel antagonist, isradipine on cognitive dysfunction in patients with schizophrenia and schizoaffective disorder. Incomplete treatment response is common. Cognitive impairment and negative symptoms persist in a majority of patients even when positive psychotic symptoms are well-controlled, and they account for a large proportion of the variance in explaining functional disability (Keefe et al. 2007). This has led to a focused effort to target the specific treatment of cognition in patients with schizophrenia (Green and Nuechterlein, 2004), with somewhat limited success to date.

Novel treatment options have been limited by an incomplete understanding of the biological etiology of schizophrenia; however, recent data from the field of genomics have provided insights into the molecular underpinnings of schizophrenia and its associated symptoms. The majority of genetic risk loci identified to date show trans-disorder effects, increasing susceptibility across a broad range of neuropsychiatric disorders including schizophrenia and bipolar disorder (Williams et al. 2011; Purcell 2009). One possible explanation for this overlap is that several of these genes are influencing risk via their effects on shared phenotypes such as neurocognitive dysfunction. One such example is a single nucleotide polymorphism (SNP; rs1006737) in the calcium channel gene, CACNA1C; initially associated with bipolar illness (Sklar et al. 2008; 2011; Ferreira et al 2008) but also linked with schizophrenia (Green et al. 2009; Nyegaard et al. 2010) and recurrent major depression (Green et al, 2009). The strength of

	Protocol Title:	A Molecular Approach to Treat Cognition in Schizophrenia: Ca 2+ Channel Blockade
	Principal Investigator Name/Contact Info:	[name] [contact]
	Primary Contact Name/Contact Info:	[name] [REDACTED]
	Date Revised:	May 16, 2017
	Study Number:	HSM# 12-0031, GCO# 12-0679, GCO# 13-1987

the association signal for CACNA1C in major mental illness is unambiguous and several subsequent studies have evaluated the effects of CACNA1C variation on neurocognitive capacity.

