### c) Number of Subjects

Up to 80 stable schizophrenia and schizoaffective patients will be recruited from the Mount Sinai Health System Outpatient Departments, and community advertisements.

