### d) Study Timelines

The recruitment and enrollment process will be active for approximately 24 months. The anticipated final date for this study is 7/2017. The patients will be informed of the length of the study, which will include 8 visits in total. There will be a screening visit, baseline visit when they will receive the study medication, a visit eight hours after the first dose of medication is taken (baseline) where blood pressure will be checked, 4 weeks of medication administration and weekly monitoring, and a visit eight hours after the dosage of the medication is increased (week 2) where blood pressure will be checked. They will be informed of all of the study procedures for each week, including assessments and medical tests.

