### e) Study Endpoints

The primary endpoint related to the efficacy of isradipine will be cognitive enhancement measured by the MATRICS Consensus Cognitive Battery (MCCB). The MCCB is accepted by the FDA as a primary outcome measure for registry trials of cognitive enhancement in schizophrenia.

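### The only feasibility criterion is the enrolment ceiling of 80: read literally, every permitted enrolment meets it, and it takes no account of MCCB completion

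*Combined protocol and SAP*

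**What the plan says.** Section 5h, which contains the data analysis plan, states that the primary analyses "will test the following hypotheses based on our specific aims". The first aim listed is "To determine the feasibility of 4 weeks of isradipine on cognitive outcomes in SZ", and the only hypothesis under it is "We will successfully recruit up to 80 stable schizophrenia and schizoaffective patients".

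The number appears in two other places, each time as a maximum. Section 1 describes a trial "in up to 80 stable outpatients with schizophrenia and schizoaffective disorder", and section 5c says "Up to 80 stable schizophrenia and schizoaffective patients will be recruited from the Mount Sinai Health System Outpatient Departments".

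Section 5d gives the recruitment period: "The recruitment and enrollment process will be active for approximately 24 months". It does not link that period to the feasibility hypothesis.

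Section 5f schedules the MCCB at baseline and week 4 only. Section 5h defines the analysis set: "All analyses will be based on an intent-to-treat sample of subjects who received at least one dose of isradipine". It then makes an exception for cognitive measures: where missing data are substantial, or a whole visit is missing, the patient's data are treated as not open to meaningful analysis.

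No section gives a minimum enrolment, an accrual rate, a completion or adherence level, or an analysis method for feasibility. The methods that follow the hypotheses in section 5h concern safety outcomes.

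**The concern.** A hypothesis that is to be tested needs some result that would count against it. Here the success criterion repeats the enrolment limit. If it is applied as worded, recruiting 10 patients supports feasibility as well as recruiting 80 does.

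The criterion is also narrower than its aim. The aim concerns four weeks of treatment studied through cognitive outcomes, whereas the criterion counts recruitment only. A patient who is enrolled and dosed but misses the week 4 visit counts towards feasibility and contributes nothing usable to the MCCB comparison. Sections 5j and 6 list several grounds on which patients are withdrawn, so the completion proportion cannot be assumed to be near 100%.

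At stake is what the feasibility result can tell anyone planning a later study. Section 8 mentions larger trials as a possible use of the results, although it does not attach that use to the feasibility aim.

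**Working it through.** **Is there a figure to reproduce?** No. The documents give no derivation of 80: no alpha, power, effect size, standard deviation or dropout allowance. The check is therefore of the rule itself, with some illustrations.

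**1. The rule as worded.** Inputs: the criterion in section 5h and the ceiling in sections 1 and 5c. Taken literally, the criterion is N ≤ 80, and the protocol permits N = 0, 1, …, 80. All 81 permitted values satisfy it. Since enrolment is capped at 80, the probability of meeting the criterion is 1.00 at any accrual rate.

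**2. The accrual needed to fill the cap.** Inputs: 80 (section 5c) and about 24 months (section 5d). 80/24 = 3.33 patients per month. This is derived here; the plan does not state it. A quarter of that rate gives 3.33/4 × 24 = 20 patients, which still satisfies N ≤ 80.

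**3. Would a rule with a floor discriminate?** Assume Poisson accrual over 24 months. The rates and floors below are assumptions, chosen only to illustrate.

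| Rate per month | Mean N | P(N ≤ 80) with the cap | P(N ≥ 40) | P(N ≥ 60) | P(N ≥ 80) |
|---|---|---|---|---|---|
| 0.5 | 12 | 1.00 | <0.001 | <0.001 | <0.001 |
| 2 | 48 | 1.00 | 0.89 | 0.05 | <0.001 |
| 3.33 | 80 | 1.00 | 1.00 | 0.99 | 0.51 |

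Only a rule with a floor separates slow from adequate recruitment. The last cell shows that the floor should not be 80 itself: a trial accruing at exactly the required rate would miss it about 49% of the time.

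**4. What a completion proportion would show.** Assume that 80% of dosed patients finish with both MCCB assessments; the documents give no figure. Clopper-Pearson 95% intervals:

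- 64/80: 69.6% to 88.1%
- 32/40: 64.4% to 90.9%
- 16/20: 56.3% to 94.3%

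These show the precision available at different enrolments. They do not measure the effect of the present wording.

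**5. Why a pass mark must say what has to reach it.** Take n = 80 and an 80% level as an example. If the point estimate must reach 80%, 64 completers are needed (64/80 = 80%). If the lower 95% limit must reach it, 72 are needed: the lower limit is 79.7% at 71/80 and 81.2% at 72/80. At a true completion rate of 80%, the binomial chance of passing is about 0.57 under the first rule and about 0.01 under the second.

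**The case against.** The strongest reply is that the literal reading is uncharitable. The word successfully suggests that the authors had 80 in mind as a goal, and a goal can be missed. That is a fair reading, so a flat claim that the feasibility aim cannot fail goes further than the text. But the documents never adopt the target reading. Every mention of 80 is as a maximum, success is not defined, and no accrual rate is stated. The ambiguity remains, and one sentence would remove it.

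A second reply is that little depends on this hypothesis. Section 1 names the effect on cognition as the primary aim, section 5e makes the MCCB the primary efficacy endpoint, and no test, stopping rule or go/no-go decision rests on feasibility. That stands, and it limits the point. A reader might infer that the defect undermines the trial's main results, or that a trial which recruited poorly would be reported as feasible. The documents support neither. The cognition and safety analyses do not use this criterion, and the number enrolled would be plain to any reader of a report.

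A third reply concerns timing. The protocol was revised on May 16, 2017, and section 5d anticipates a final date of 7/2017. The trial is open label, and section 5i has safety outcomes summarised after every five completers. The team may well know the accrual and completion counts already, although the documents do not say so. A new pass/fail level would then be hard to set blind to those counts. This stands too, and it favours descriptive reporting at this stage.

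**Conclusion.** The point holds for the feasibility conclusion. A primary hypothesis is stated whose only criterion is the enrolment cap. Followed as written, it can be declared met at any of the 81 permitted enrolments, and it omits the completion that section 5h itself requires before cognitive data can be used. This is a fault in a stated rule and not merely a missing detail.

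It would be tempting to read 3.3 per month as the protocol's own recruitment target and to judge the trial against it. The documents do not support that: the rate is only what would fill the cap in about 24 months, and it serves as a reference value.

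The finding on the wording needs no assumption beyond the literal reading. The accrual probabilities assume Poisson recruitment at invented rates, and the completion intervals assume 80% completion. Both are illustrations.

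**What to change.** In section 5h, state that 80 is the enrolment cap and stop presenting it as a hypothesis that can be confirmed. Estimate feasibility from data the trial already collects:

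- (a) the number enrolled and the monthly accrual over the recruitment period, set beside the 3.3 per month needed to fill the cap;
- (b) the proportion of dosed patients who complete week 4 with both MCCB assessments, with an exact 95% CI.

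If the sponsor wants a pass/fail level, it should be a justified minimum below the cap. The plan should say whether the point estimate or the lower confidence limit must reach it, and the level should be dated and fixed before the counts are known. If that is no longer possible, report (a) and (b) descriptively and do not claim a confirmed hypothesis.

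The cost is wording only: no new visits, patients or measurements. The downside is that the feasibility result may turn out unfavourable, or may be only descriptive.

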Along with closely monitoring for symptom exacerbation, each visit with the study physician will entail a detailed side effect evaluation, which will include vital signs and a side effect checklist. The most common side effects of isradipine include hypotension, edema, headache, dizziness, palpitations, fatigue, flushing, and constipation. Patients will be educated about the potential for hypotension and its symptoms, and blood pressure and symptoms will be measured at every visit. If the patient develops clinically significant hypotension (e.g., systolic blood pressure equal to or less than 90 mm Hg or diastolic equal to or less than 60 mm Hg, or if they experience significant associated symptoms), or if at any point in the study subsequent to baseline there is a blood pressure drop of 20% or more from blood pressure at baseline, they will be discontinued from the study medication and excluded from the protocol. Rare side effects have also been reported including arrhythmias, syncope, severe hypotension or myocardial infarction. The informed consent process will alert subjects to these potential risks and close monitoring will ensure prompt response to any adverse effects with appropriate treatment and/or study discontinuation, as indicated.

Additional risks are minimal and involve the completion of questionnaires, interviews and paper-pencil/computerized tests. Some of the questions may be distressing to the individual and subjects will be told that they may refuse to answer any questions that they so choose. The testing procedure can sometimes cause fatigue but we will ensure plenty of resting periods during the session and will instruct subjects to notify staff if they would like an additional break. Pain and bruising may be associated with the blood draw for screening labs; however, a trained phlebotomist will perform the procedure to avoid any additional discomfort.

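### The primary safety hypothesis makes a non-significant side-effect comparison the favourable result, with no acceptable rate or interval, so safety is supported more easily the fewer patients are rated

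*Combined protocol and SAP*

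**What the plan says.** The analysis plan sits in section 5h (Data Management and Confidentiality). Under its primary analyses, the safety aim carries the hypothesis "The frequency of new or worsened side effects (clinician-rated; self-reported; lab-based) will not be significantly different from baseline to end of study visit". The test follows: "A Fisher exact test will compare time-points by frequencies of new or worsened (compared with baseline) side effect severity ratings", and "this will be done for all side effects assessed by the SEC". Laboratory measures get a repeated measures ANCOVA (baseline and week 4), and blood pressure a mixed model over the weekly visits.

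Sample size appears only as a ceiling. Section 5c says "Up to 80 stable schizophrenia and schizoaffective patients will be recruited", and section 1 describes a "4-week open label cognitive enhancement trial of isradipine in up to 80 stable outpatients". There is no control arm. The protocol states no significance level, power, minimum enrolment, acceptable side-effect rate, margin or confidence interval for side-effect frequency.

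The analysis set in section 5h is everyone who took at least one dose, but no rule covers an SEC rating missing at the end-of-study visit. Section 5j discontinues patients for clinical worsening or any SAE. For patients who meet the blood pressure criteria, section 6 says "they will be discontinued from the study medication and excluded from the protocol". By section 5f, the SEC and the self-report form are completed at all visits.

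**The concern.** The hoped-for result is that frequency "will not be significantly different from baseline to end of study visit". That puts the null hypothesis in the place of the conclusion. A non-significant test can mean that side effects did not increase, or that too few patients were rated to show that they did, and the planned analysis cannot separate the two. With no rate or interval to judge against, the favourable result becomes easier to reach as enrolment falls or as affected patients leave before week 4.

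The stake is the trial's safety statement, which belongs to one of its listed primary hypotheses. Section 6 names hypotension, edema, headache, dizziness and other symptoms as common with isradipine but gives no rates. The useful question is therefore how frequent they were and how high the true rate could be, and a p-value above 0.05 does not answer it.

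**Working it through.** The plan has no figure to reproduce, so the check is how the stated test behaves.

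**Inputs.** The test is Fisher's exact test per SEC item, comparing time-points (section 5h). The sample size n is at most 80 (section 5c); 10, 20, 40 and 80 are examined. *Assumed, because not stated:* two-sided 0.05; true new-or-worsened rates of 10% to 20%; the shares of affected patients who leave early. The baseline count is taken as zero because new or worsened is defined relative to baseline.

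**Step 1: largest count Fisher does not flag.** For x/n against 0/n with equal n, the two-sided p is 2 × C(n,x)/C(2n,x). For n = 20:
- x = 4: 2 × 4,845/91,390 = 0.106, not flagged.
- x = 5: 2 × 15,504/658,008 = 0.047, flagged.

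| n | Largest unflagged x (p) | Next x (p) | Rate at largest unflagged x, exact 95% CI |
|---|---|---|---|
| 10 | 4 (0.087) | 5 (0.033) | 40%, 12-74% |
| 20 | 4 (0.106) | 5 (0.047) | 20%, 6-44% |
| 40 | 5 (0.055) | 6 (0.026) | 12.5%, 4-27% |
| 80 | 5 (0.059) | 6 (0.028) | 6%, 2-14% |

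The permitted count hardly moves with n, so the permitted rate rises steeply as n falls.

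**Step 2: chance that a real side effect goes unflagged.** This is P(X ≤ c), with X ~ Binomial(n, true rate) and c the largest unflagged count above.

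| True rate | n = 10 | n = 20 | n = 40 | n = 80 |
|---|---|---|---|---|
| 10% | 99.8% | 96% | 79% | 18% |
| 15% | 99% | 83% | 43% | 1.4% |
| 20% | 97% | 63% | 16% | 0.1% |

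At one-sided 0.05, the 20% row becomes 88%, 63%, 8% and below 0.1%.

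**Step 3: another reading of the test.** If Fisher instead compares symptom prevalence at the two visits, treated as independent samples, a rise from 5% to 15% goes unflagged 99%, 93%, 82% and 52% of the time at n = 10, 20, 40 and 80.

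**Step 4: missing week-4 ratings.** Take 80 dosed patients and a true rate of 15%, so 80 × 0.15 = 12 affected are expected. With all rated at week 4, the chance of no flag is 1.4%.
- Half of the affected leave: 22% if the week-4 patients are compared with 0/80 at baseline. If baseline is restricted to the same patients, P(X ≤ 5) with X ~ Binomial(80, 0.15 × 0.5 = 0.075) is 44%.
- Four fifths of the affected leave: 80% and, with X ~ Binomial(80, 0.15 × 0.2 = 0.03), 97% on the same two readings.

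These leaving shares are illustrations, not forecasts.

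**Step 5: what an interval would show.** With zero events, the exact 95% upper limit is 1 − 0.025^(1/n): 30.8% at n = 10, 16.8% at 20, 8.8% at 40 and 4.5% at 80. A small trial then shows its own uncertainty instead of gaining from it.

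**The case against.** *No sentence says that safety will be concluded if p exceeds 0.05.* This is correct. A reader might infer an explicit decision rule, but section 5h states an expected result as a hypothesis. What stands is that the expected result is non-significance and no other criterion for side-effect frequency is given, so the rule is implied.

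*At full enrolment common side effects are caught.* This largely stands. A reader might infer that common side effects will slip through this trial whatever its size. With 80 patients, complete week-4 ratings and a zero baseline, a 15% effect is missed only 1.4% of the time and a 20% effect 0.1%. The documents do not predict a trial of 10 or 20; they set no floor.

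*A paired test would be more lenient.* A reader might note that a paired exact test needs six worsened patients (five gives 2 × 0.5^5 = 0.0625), so that 5/20, or 25%, would pass. The plan specifies Fisher, under which 5/20 gives p = 0.047 and is flagged. The paired figure does not describe the plan as written.

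*Other safety provisions exist.* Blood pressure is modelled over all weekly visits, adverse events are recorded, safety is summarised after every five completers (section 5i), and section 6 has stopping criteria. These protect individual patients and add evidence, but do not say what side-effect frequency would count as acceptable.

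*The downstream harm is limited.* Section 8 mentions larger pivotal trials when discussing benefits. It does not say they would rely on this trial's safety verdict, so the point is not rested on that.

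**Conclusion.** The concern holds in a bounded form. The hypothesis implies that a non-significant Fisher test supports safety, which it cannot do without a stated rate or interval. The effect is serious if enrolment falls well short of 80: at n = 20 an observed 20% goes unflagged, and a true 10% rate is missed 96% of the time. At a complete 80 it is modest: the largest unflagged rate is 6%, and a true 10% rate is missed 18% of the time. Patients discontinued for worsening, an SAE or blood pressure may have no week-4 rating, which would raise the chance of a miss even at 80; by how much cannot be known from the documents.

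The figures rest on two-sided 0.05, one item at a time and a zero baseline count, none of which the protocol states in those terms. The flaw in the criterion does not depend on them. The cognitive endpoint is unaffected.

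**What to change.** Remove non-significance as the safety criterion in section 5h and replace it with estimation:

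- **SEC and self-report items:** give the number and percentage of all dosed patients with a new or worsened rating at any post-baseline visit, with an exact 95% CI. Count early leavers by the ratings they have. Base the safety statement on the upper limit.
- **Laboratory and vital-sign measures:** give the mean change with a 95% CI from the models already planned.
- **If a yes/no verdict is wanted:** state the largest acceptable rate before the data are summarised and require the upper limit to fall below it. The trial is open label and safety is reviewed after every five completers, so a rate chosen late gives limited protection and its timing should be disclosed.

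The cost is wording in the analysis section. No new visits, data or patients are needed, because the ratings are already taken at all visits. The price is a less favourable conclusion in a small sample. In a single arm the rates also include background symptoms unrelated to the drug, and the report should say so.
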